## **SUMMARY OF CHANGES**

The following changes have been introduced in this Version 2.0 of the protocol (dated 01 Jul 2021) and are given as a combination of double underlined and italic text. Deleted text is given as double strikethrough.

The rationale for these changes is the change in blood sample volumes and timepoints, and changes in the reporting of metabolite profiling/identification and PK. In addition, contact information of the Client's Clinical Project Manager has been altered.

The changes can be found in:

- [Contact Information](#)
- [Synopsis](#)
- [Table 1 - Schedule of Assessments](#)
- [Section 3.5.1.3 Total Blood Volume: Table 3 - Number and Volume of Blood Samples and Total Blood Volume Collected per Subject](#)
- [Section 3.5.3.3 Exploratory Variables](#)
- [Section 3.5.4 Drug Concentration Measurements](#)
- [Section 3.6.2.1 Pharmacokinetic Evaluation](#)
- [Section 3.6.2.3 Evaluation of Exploratory Variables](#)

## SYNOPSIS

### Study Title

A SINGLE-CENTER, OPEN-LABEL STUDY TO INVESTIGATE MASS BALANCE, EXCRETION PATHWAYS AND METABOLITES AFTER A SINGLE ORAL DOSE OF 500 MG, 3.7 MBq, [C]BTZ-043 IN HEALTHY MALE VOLUNTEERS

### Study Codes

Sponsor code : LMU-IMPH-BTZ-043-03  
PRA code : NVS543EC-185431  
EudraCT number : 2021-000449-42

### Objectives

Primary : To determine the rates and routes of excretion of [C]BTZ-043-related radioactivity, including mass balance of total drug-related radioactivity in urine and feces (and vomit, if applicable), following the oral administration of a single 500 mg dose of [C]BTZ-043 in healthy male volunteers.  
: To determine the pharmacokinetics (PK) of total radioactivity in blood and in plasma.  
: To characterize the plasma PK of BTZ-043 and main metabolites by liquid chromatography-mass spectrometry (LC-MS), if applicable.  
: To characterize the urine concentrations of BTZ-043 and main metabolites by LC-MS, if applicable.  
Secondary : To assess the safety and tolerability of a single 500 mg oral dose of BTZ-043 administered to healthy volunteers.  
Exploratory : To identify BTZ-043's metabolites in plasma, and to quantify metabolites not measured in the primary objectives by radiometry in order to elucidate key biotransformation pathways and clearance mechanisms of BTZ-043 in humans.

: To identify BTZ-043's metabolites in excreta (urine and feces) and to quantify metabolites not measured in the primary objectives by radiometry in order to elucidate key biotransformation pathways and clearance mechanisms of BTZ-043 in humans.

### Design and Treatments

This study is a Phase 1, single-center, open-label study to investigate the absorption, metabolism, and excretion of BTZ-043 after a single oral administration of 500 mg BTZ-043 containing 3.7 MBq of [C]BTZ-043 in 4 healthy adult male subjects.

A total of 4 evaluable subjects completing all procedures are required. Six (6) subjects will be enrolled in the cohort in order to have 4 evaluable subjects. If the cohort of 4 subjects administered with 500 mg BTZ-043 containing 3.7 MBq of [C]BTZ-043 leads to less than 4 evaluable subjects, the 2 back-up subjects can be dosed subsequently to ensure that 4 subjects have completed all study procedures and are evaluable. If any of the 4 subjects vomits within 4 hours after study drug administration (approximately 2 times the median Tmax of BTZ-043), the subject will be replaced. The 2 back-up subjects will stay in the clinical research center until the morning of Day 2.

The study will consist of a screening period (Day -21 to -2), a baseline period (Day -1), a single dose treatment on Day 1 with a minimum of 96 hours (=4 days) post dose in-house observation period (Days -1 up to afternoon Day 5), and a follow-up visit 30 days ( $\pm$ 2 days) after the [C]BTZ-043 dose. The subjects will be admitted to the clinical site on Day -1, at least 17 hours before the administration of [C]BTZ-043 for baseline evaluation. Subjects will be administered a single 500 mg [C]BTZ-043 dose as drinking suspension. Subjects will be confined to the clinical site for at least 96 hours following drug administration (ie, afternoon of Day 5). During this time, blood, feces, and urine samples for measurement of [C]BTZ-043 and metabolites will be collected. The radioactivity excreted in urine and feces as well as radioactivity in blood and plasma should be measured and the data should be communicated daily to [name] or his designee. The subjects will be released from the clinic approximately 96 hours to 168 hours after dose administration and upon satisfactory recovery of radioactivity (at least 90%) approved by the Sponsor's scientific advisor after consultation of the Sponsor. This will depend on the radioactivity excretion balance as assessed by a normal counting method or real time rapid analysis on site ('quick counting' procedure, utilizing liquid scintillation counter, or sample combustion apparatus) of radioactivity in plasma, urine, and feces accumulated until 96 hours, as feasible. The data has to be available before subjects will be released from the clinic.

The in-house period should be prolonged up to the morning of Day 8 if at least 1 of the following applies:

- Total radioactivity in plasma is higher than 5% of total radioactivity-Cmax and/or PK parameters for determination of the total radioactivity-elimination phase cannot be determined reliably.
- The mass balance in urine and feces is not complete by Day 5 (ie, <90%).
- The combined urinary and fecal excretion is not  $\leq$ 1% of the administered dose per 24 hours for 2 consecutive days based on C-radioactivity "quick counts" or normal counts, as feasible.

In the event of an incomplete mass balance on the morning of Day 8, subjects may be discharged from the clinical site upon discretion of the Investigator. Subjects with an incomplete mass balance (<90% of dose administered and/or combined urinary and fecal excretion >1% of the administered dose per 24 hours for 2 consecutive days based on C-radioactivity "quick counts" or normal counts, as feasible) on Day 8 will be asked to return to the clinical site for one or two 24-hour visits (Day 11-12 and Day 15-16).

In the event of subjects not defecating for 2 days, measures will be taken to ensure defecation (eg, additional fibers, plum juice, dried prunes, and/or sufficient hydration).

### **Study Schedule**

Screening	: Between Day -21 and Day -2.
Treatment period	: From Day -1 (admission) to approximately 96 hours after study drug administration (Day -1 up to afternoon Day 5) with possible extension (Day 6 to Day 8) as well as possible 24-hour visits (Day 11-12, Day 15-16).
Follow-up	: 30 days ( $\pm 2$ days) after the [  C]BTZ-043 dose.

### **Subjects**

4 healthy male subjects

### **Main Criteria for Inclusion**

Age	: 18 years to 55 years, inclusive, at screening
Weight	: 55 to 90 kg, inclusive, at screening
Body mass index	: 18.0 to 29.0 kg/m  , inclusive, at screening

### **Study Drug**

#### Active Medication

Active substance	: BTZ-043
Activity	: Inhibition of Mycobacterium tuberculosis DprE1
In development for	: Tuberculosis
Dose	: 1 x 100 mL (equivalent to 500 mg BTZ-043)
Strength	: 5 mg/mL BTZ-043 containing 0.037 MBq/mL of [  C]-BTZ-043
Dosage form	: Oral suspension
Manufacturer	: Prepared by pharmacy at PRA

### **Variables**

Safety	: Adverse events, clinical laboratory, vital signs, 12-lead electrocardiogram, physical examination
Pharmacokinetics	: Total radioactivity concentrations in plasma, whole blood, urine, and feces Total radioactivity in plasma and whole blood PK parameters estimated using noncompartmental analysis, as appropriate : C max , t max , t 1/2 , AUC inf , AUC 0-t , and whole blood to plasma ratios Concentrations of BTZ-043 and main metabolites in plasma and urine Plasma and urine BTZ-043 PK parameters estimated using noncompartmental analysis, as appropriate: C max , t max , t 1/2 , k el , AUC inf , AUC 0-t , CL/F, V z /F, Ae urine , Fe urine , and CL r Plasma and urine metabolites PK parameters estimated using noncompartmental analysis, as appropriate: C max , t max , t 1/2 , k el , AUC inf , AUC 0-t , Ae urine , and Fe urine Urine and feces (and vomit, if available) radioactivity PK parameters estimated using noncompartmental analysis, as appropriate: Ae urine , Fe urine , Ae feces , Fe feces , and, if available, Ae vomit , and Fe vomit
Exploratory	: Metabolite profiles, metabolite identification, as feasible %AUC total radioactivity of BTZ-043 and metabolites

**Statistical Methods**

Safety parameters : Descriptive statistics

PK parameters : Descriptive statistics for all relevant PK parameters: n, number of missing values to be reported (m), geometric mean, geometric coefficient of variation, mean, coefficient of variation, SD, median, minimum, and maximum

Exploratory parameters : Descriptive statistics

**Table 1 Schedule of Assessments**

Visit	Screening							Treatment Period a							24-hour Visits a			Follow-up	
	Study Day	Days -21 to -2	Day -1	Day 1	Day 2	Day 3	Day 4	Day 5	Day 6 m	Day 7 m	Day 8 m	Day 11 m	Day 12 m	Day 15 m	Day 16 m	Day 31 (±2 days)			
Confinement a		X	X	X	X	X	X	X	(X)	(X)	(X)	(X)	(X)	(X)	(X)	(X)			
Ambulatory	X																X		
Admission		X															(X)		
Discharge b								X	(X)	(X)	(X)	(X)	(X)	(X)	(X)	(X)			
Informed Consent	X																		
Medical History	X																		
Demographics	X																		
Physical Examination c	X	X																X	
Body Weight	X	X																	
Height and BMI	X																		
Calculation																			
Serology (HBsAg, anti-HCV, anti-HIV 1 and 2)	X																		
SARS-CoV-2 PCR d	X	X																(X)	
Drug and Alcohol Screen	X	X																X	
Clinical Laboratory e	X	X																X	
Urinalysis	X	X																X	
12-lead ECG f	X	X	X	X	X	X	X	X	X	(X)	(X)	(X)	(X)	(X)	(X)	(X)		X	
Vital Signs g	X	X	X	X	X	X	X	X	(X)	(X)	(X)	(X)	(X)	(X)	(X)	(X)		X	
Eligibility Check	X	X	X	X															
Study Drug Administration																			
Plasma Sampling for BTZ-043 and Main Metabolites h		X	X	X	X														
Whole Blood Sampling for Radioactivity i		X	X	X	X														
Plasma Sampling for Total Radioactivity and Metabolite Profiling i		X	X	X	X														

Visit	Screening							Treatment Period a							24-hour Visits a			Follow-up
	Study Day	Days -21 to -2	Day -1	Day 1	Day 2	Day 3	Day 4	Day 5	Day 6 m	Day 7 m	Day 8 m	Day 11 m	Day 12 m	Day 15 m	Day 16 m			
Urine Collection and Pooling for BTZ-043 and Main Metabolites, Total Radio activity, and Metabolite Profiling j		X	X	X	X	X	X	X	(X)	(X)	(X)	(X)	(X)	(X)	(X)	(X)		
Feces Collection for Total Radioactivity and Metabolite Profiling k	X	X	X	X	X	X	X	(X)	(X)	(X)	(X)	(X)	(X)	(X)	(X)	(X)		
Vomit Collection for Total Radioactivity, if available l			X															
Previous and Concomitant Medication	X	X	X	X	X	X	X	(X)	(X)	(X)	(X)	(X)	(X)	(X)	(X)	(X)		
AE Monitoring	X	X	X	X	X	X	X	(X)	(X)	(X)	(X)	(X)	(X)	(X)	(X)	(X)		

AE=adverse event; BMI=body mass index; ECG=electrocardiogram; HBsAg=hepatitis B surface antigen; HCV=hepatitis C virus; PCR=polymerase chain reaction; PK=pharmacokinetic(s)

a Subjects will be in the clinic from Day -1 (predose) until Day 5 with possible extension (Day 6 to Day 8) as well as possible 24-hour visits (Day 11-12, Day 15-16). The 2 back-up subjects will stay in the clinic until the morning of Day 2.

b Subjects will be released from the clinic 96 hours after dose administration and upon satisfactory recovery of radioactivity.

c Complete physical examinations will be conducted at screening, Day -1, and follow-up/early termination. Symptom driven physical examinations may be conducted at any time, per the investigator's discretion.

d Sampling of nasal and throat mucosal cells. If deemed necessary, additional tests may be conducted during the study. The nonclinical project manager will be informed immediately upon availability of Day 11 results, as this will qualify the feces samples for metabolite profiling with regard to potential COVID-19 infectivity.

e Clinical laboratory tests (including clinical chemistry, hematology, and urinalysis): at screening; on Day -1 (admission), Day 2, and Day 4; and at follow-up.

f 12-lead ECG: at screening; Day -1 and 1 hour, 4 hours, and 24 hours postdose; at discharge; and at follow-up.

g Vital signs (supine systolic and diastolic blood pressure, pulse, body temperature, and respiratory rate): at screening; at admission; at predose and at 1 hour, 4 hours, and 24 hours postdose; at discharge; and at follow-up.

h Plasma sampling for PK of BTZ-043 and main metabolites in plasma, at predose and 0.25, 0.5, 1, 1.5, 2, 3, 5, 8, 12, 16, 24, 36, and 48 hours postdose.

i Total radioactivity in whole blood and plasmal: at predose and 0.25, 0.5, 1, 1.5, 2, 3, 5, 8, 12, 16, 24, 36, 48, 72, and 96 hours postdose (in case total radioactivity recovered is still <90%: in addition 120, 144, and 168 hours postdose and at further 24-hour visits [264 and 360 hours postdose until study completion]). Metabolite profiling in plasma, at predose and 0.25, 0.5, 1, 1.5, 2, 3, 5, 8, 12, 16, 24, 36, 48, 72, and 96 hours postdose (in case total radioactivity recovered is still <90%: in addition 120, 144, and 168 hours postdose).

j Urine collection and pooling for BTZ-043 and main metabolites, total radioactivity, and metabolite profiling: at predose (within 12 hours prior to dosing) and over 0-24, 24-48, 48-72, and 72-96 hours postdose collection intervals (in case total radioactivity recovered is still <90%, in addition 96-120, 120-144, and 144-168 hours postdose and at further 24-hour intervals [Day 11-12 and Day 15-16] until study completion).

k Feces collection for total radioactivity and metabolite profiling; predose feces collection to be collected at any time within 48 hours prior to study drug administration (at home or in the clinic). After administration of BTZ-043, feces will be collected in 24 hour collection intervals up to 96 hours postdose (in case total radioactivity recovered is still <90%: in addition 120, 144, and 168 hours postdose and at further 24-hour intervals [Day 11-12 and Day 15-16] until study completion).

l If produced, vomit will be collected up to 8 hours after the administration of the study drug for total radioactivity determination.

m Day 6-8 procedures will only be conducted in case that the recovery of radioactivity was not satisfactory until Day 5. 24-hour visits procedures will only be conducted in case that the recovery of radioactivity was not satisfactory until Day 8. For the 24-hour visits (if applicable): feces collection to be collected at home within 48 hours prior to admission.

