## 2. OBJECTIVES

### 2.1 Primary

- To determine the rates and routes of excretion of [C]BTZ-043-related radioactivity, including mass balance of total drug-related radioactivity in urine and feces (and vomit, if applicable), following the oral administration of a single 500 mg dose of [C]BTZ-043 in healthy male volunteers.
- To determine the PK of total radioactivity in whole blood and in plasma.
- To characterize the plasma PK of BTZ-043 and main metabolites by liquid chromatography-mass spectrometry (LC-MS), if applicable.
- To characterize the urine concentrations of BTZ-043 and main metabolites by LC-MS, if applicable.

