##### 3.1.3 Treatment Period

Subjects will be admitted to the clinical research center on Day -1, which is the day prior to Day 1, the day of drug administration.

Subjects will receive a single oral dose of 500 mg BTZ-043 containing 3.7 MBq of [C]BTZ-043 on Day 1. Subjects will be discharged from the clinical research center on Day 5 (approximately 96 hours after drug administration) upon satisfactory recovery of radioactivity. If the criteria for discharge are not met on Day 5, subjects will be required to remain confined for a maximum of 3 additional days (Days 6 to 8) until the criteria are met (daily check by quick counts or normal counts, as feasible). The in-house period should be prolonged up to the morning of Day 8 if at least 1 of the following applies:

- Total radioactivity in plasma is higher than 5% of radioactivity-Cmax and/or PK parameters for determination of the total radioactivity-elimination phase cannot be determined reliably.
- The mass balance in urine and feces is not complete by Day 5 (ie, >90%).
- The combined urinary and fecal excretion is not ≤1% of the administered dose per 24 hours for 2 consecutive days based on C-radioactivity “quick counts” or normal counts, as feasible.

If the criteria for discharge are still not met on Day 8, subjects may be discharged from the clinical site upon discretion of the Investigator. To ensure that adequate consideration is given to the protection of the subject's interests, subjects with an incomplete mass balance on Day 8 will be asked to return to the clinical site for one or two 24-hour visits (Day 11-12 and Day 15-16).

On the day of study drug administration (Day 1), an FDA-recommended high-fat (or a standardized breakfast, if applicable, as outlined in Section 3.4.4 and Section 3.4.7) with calculated caloric content will be provided.

Assessments during the treatment period will be performed as presented in the schedule of assessments (Table 1).

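### The criteria that keep or recall a subject after 96 h differ from the condition that schedules sampling after 96 h, so it is unclear whether a subject held with recovery of at least 90% gives late blood and plasma samples

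*Protocol*

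**What the plan says.** **Stay.** The Protocol Synopsis (Design and Treatments) states: "The in-house period should be prolonged up to the morning of Day 8 if at least 1 of the following applies". The three criteria are:

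1. plasma total radioactivity above 5% of its Cmax, and/or, as Protocol 3.1.3 also has it, "PK parameters for determination of the total radioactivity-elimination phase cannot be determined reliably";
2. recovery in urine and feces below 90%;
3. combined excretion not down to 1% of dose or less per 24 h for two consecutive days.

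Protocol 3.1.3 and SAP 5.0 repeat the list.

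**Recall.** The Synopsis asks a subject back for Days 11-12 and 15-16 on recovery below 90% and/or "combined urinary and fecal excretion >1% of the administered dose per 24 hours for 2 consecutive days". Protocol 3.1.3 and SAP 5.0 say only that the mass balance is incomplete.

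**Sampling.** Protocol 3.5.1.1.1 takes blood at the Table 1 time points. Footnote i lists radioactivity samples to 96 h and adds more "in case total radioactivity recovered is still <90%: in addition 120, 144, and 168 hours postdose", with 264 and 360 h under the same condition. Footnote j adds urine "in case total radioactivity recovered is still <90%, in addition 96-120, 120-144, and 144-168 hours postdose", and footnote k has the same trigger for feces. Footnote m reads: "Day 6-8 procedures will only be conducted in case that the recovery of radioactivity was not satisfactory until Day 5". SAP Appendix 2 repeats all four. The Synopsis glosses satisfactory recovery as at least 90%.

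**Objective.** Protocol 2.1 lists as primary: "To determine the PK of total radioactivity in whole blood and in plasma".

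**The concern.** Three criteria can keep a subject in the clinic, but only one of them also triggers the scheduled sampling. The mismatch matters most for the plasma criterion, mainly its second limb. A subject may be kept because the elimination phase of total radioactivity is not resolved, and only later plasma or blood samples can resolve it. If his recovery is already at least 90%, footnote i schedules none. The longer stay would then not serve its stated reason, and half-life and AUCinf of total radioactivity would rest on data to 96 h. With four subjects, one poorly determined value is a quarter of each mean.

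**Working it through.** **1. Sample counts.** Footnote i gives predose plus 15 times to 96 h, which is 16. Adding 120, 144 and 168 h gives 19, and adding 264 and 360 h gives 21. Table 3 allows 21 samples for total radioactivity in plasma and 21 in whole blood, so it budgets for the full extension.

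**2. Triggers side by side.** Each of the three criteria can be met or not, giving 8 combinations. For this count the excretion-rate condition is treated as the same in the stay and recall rules.

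- Stay: 7 of 8 combinations hold the subject. In 3 of those 7 (plasma only, excretion rate only, or both, with recovery at least 90%) the footnotes trigger no sampling after 96 h.
- Recall, as the Synopsis defines it: 6 of 8 combinations recall the subject. In 2 of those 6 (excretion rate with or without plasma, recovery at least 90%) the footnotes trigger no sampling at the return visits.

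These are counts of logical cases, not probabilities.

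**3. Precision of the terminal slope (illustration).** For a log-linear fit with constant log-scale error, SE(kel) is proportional to 1/√S, where S = Σ(t − t̄)². The factor by which SE(kel) is larger without the late samples is √(S with late samples / S to 96 h).

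| Terminal phase starts | S to 96 h | with 120 h | with 120, 144 h | with 120, 144, 168 h |
|---|---|---|---|---|
| 24 h | 3341 | 6840 (1.43) | 12055 (1.90) | 19278 (2.40) |
| 36 h | 2124 | 4723 (1.49) | 8760 (2.03) | 14523 (2.61) |
| 48 h | 1152 | 2880 (1.58) | 5760 (2.24) | 10080 (2.96) |

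For the 48 h row, times 48, 72 and 96 give S = 24² + 0 + 24² = 1152; all six times give 10080; √(10080/1152) = 2.96. The factor falls to 1 if no late sample is quantifiable. The start times are assumptions, because SAP 15.2.2 selects terminal points automatically.

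**4. Excreta.** If recovery is at least 90% at 96 h and total recovery cannot exceed 100%, the amount missed afterwards is at most 100 − 90 = 10 percentage points of dose.

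**5. Blood volume.** Table 3 prints deleted and new values together. Read as revised, it reproduces its own total: 14×2 + 21×4 + 21×1 + 19×15 + 14 + 12 + 5 = 28 + 84 + 21 + 285 + 31 = 449 mL. The part that does not depend on the extension is 28 + 31 = 59 mL. Each time point to 168 h takes 4 + 1 + 15 = 20 mL.

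- To 96 h: 59 + 16×20 = 379 mL.
- To 168 h: 59 + 19×20 = 439 mL, which is 60 mL more.
- Total radioactivity only after 96 h: 379 + 3×5 = 394 mL.

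Table 3 counts four chemistry and four hematology draws, but footnote e lists five occasions (screening, Day -1, Day 2, Day 4, follow-up). One more costs 3.5 + 3 = 6.5 mL, giving 385.5 and 445.5 mL, and 455.5 mL for the full schedule with 264 and 360 h.

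**The case against.** Several passages point towards continued sampling:

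- The Synopsis asks that radioactivity in blood and plasma be measured and the data communicated daily, with no recovery condition.
- Protocol 3.1.3 and SAP 5.0 keep the subject "until the criteria are met (daily check by quick counts or normal counts, as feasible"). The plasma criterion cannot be rechecked without plasma, nor the excretion-rate criterion without later urine and feces.
- The SAP Appendix 2 grid shows conditional marks on Days 6 to 8 for both radioactivity rows.
- Protocol 3.5.1.3 lets the investigator or sponsor add blood samples up to 500 mL.
- Footnotes i, j and k state a case for sampling without the word only. That word stands in footnote m, whose recovery wording might be meant to cover all the discharge criteria; the Synopsis itself counts excretion rate under incomplete mass balance.

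This stands to the extent that a careful site might well sample. But none of these passages schedules a 120, 144 or 168 h sample when recovery is at least 90%. The request for daily data sets no times and follows a sentence about a stay of at least 96 h. The grid marks fall under footnotes i and m, the extra blood is discretionary, and the gloss of satisfactory as at least 90% favors the narrow reading of footnote m. The text therefore gives two different instructions.

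It is also fair that SE(kel) is not a planned output, that a subject held only for plasma above 5% of Cmax may already have a reliable half-life, and that the case is narrow in a descriptive study of four subjects.

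**Conclusion.** The triggers for staying, for recall and for sampling conflict as printed, and the conflict is worth removing. If the site follows footnote i, a subject held on the plasma criterion with recovery of at least 90% has 16 rather than 19 total-radioactivity time points per matrix and gains no terminal-phase data. The loss of slope precision ranges from none to a factor of 2.4 to 3.0, depending on how many late samples are quantifiable. That range assumes constant log-scale error and a terminal phase starting between 24 and 48 h. The documents do not show how likely such a subject is.

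Three stronger readings are tempting but not supported:

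- A reader might infer that such a subject certainly gives no late plasma or blood. The daily measurement and daily check leave that open.
- A reader might infer that his half-life would have to be reported as not calculated under the three-point rule in SAP 15.2.2. That rule refers to numeric points in the profile, which may hold many by 96 h. It is also attributed to a Nuvisan procedure, while SAP 2.0 assigns total radioactivity to ICON/PRA.
- A reader might infer that the mass balance is compromised. The footnotes conflict for excreta in the same way, but the missed amount is at most 10 percentage points of dose under the assumption above.

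**What to change.** Reconcile footnotes i, j, k and m of Protocol Table 1 and SAP Appendix 2 with the stay criteria (Protocol Synopsis, Protocol 3.1.3, SAP 5.0) and the recall criteria (Protocol Synopsis). Each condition that keeps or recalls a subject should also trigger the matching blood, plasma, urine and feces collection, whichever criteria the sponsor keeps. In the same edit, reconcile the recovery bullet in Protocol 3.1.3, which prints >90% where the Synopsis and SAP 5.0 print <90%. That is a minor wording point.

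The cost is wording in both documents. If the sponsor widens sampling, an affected subject gives at most 60 mL more blood by 168 h, or 15 mL more if only total radioactivity is sampled. The totals stay below the 500 mL ceiling on either count of laboratory draws, and Table 3 already allows for the samples. If the stay criteria are narrowed instead, no blood is added.
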